1.3.2.2 Evaluation of Tumour Response

Tumour response will be evaluated by the site investigator and by an independent central review. The central review will be the data used for all imaging efficacy endpoints. Response and progression will be evaluated using the revised RECIST guideline (v1.1) and CCI [REDACTED]. Only subjects with measurable disease at baseline, who have received at least one cycle of therapy, and have had their disease re-evaluated will be considered evaluable for response.

All measurable lesions up to a maximum of two lesions per organ and five lesions in total, representative of all involved organs, should be identified as target lesions and recorded and measured at baseline. Target lesions should be selected on the basis of their size (lesions with the longest diameter), be representative of all involved organs, and permit reproducible repeated measurements. On occasion, if the largest lesion does not permit reproducible measurement, the next largest lesion which can be measured reproducibly will be selected. A sum of the diameters (longest for non-nodal lesions, short axis for nodal lesions) for all target lesions will be calculated and reported as the baseline sum diameters. If lymph nodes are included in the sum, then only the short axis will be added into the sum. The baseline sum of diameters will be used as reference to further characterise any objective tumour regression in the measurable dimension of the disease.

All other lesions (or sites of disease) including any measurable lesions over and above the five target lesions should be identified as nontarget lesions and should also be recorded at baseline. Measurements of these lesions are not required, but the presence, absence, or unequivocal progression of each should be noted throughout follow-up.

Overall objective tumour response will be classified as CR, PR, SD or PD, and unevaluable according to RECIST v1.1 at each visit. Based on objective tumour response, BOR, ORR, DoR and DCR will be calculated for both the central and the investigator review.

Time to PFS according to RECIST v1.1 will also be summarised.

Details of the response evaluation will be given in a separate image review charter.

CCI

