The DCR is defined as the proportion of participants who achieved a Complete Response (CR), a Partial Response (PR) or a Stable Disease (SD) as best overall response according to RECIST v1.1 criteria in the ITT Set. Subjects with no tumour assessment after the start of study treatment will be considered as with no disease control.

- Sum of diameters as percentage change

- Percentage change from baseline in the target lesions identified in the RECIST v1.1 assessment and/or the initial lesion(s) identified at eligibility as being >20 mm in diameter, calculated as:

$$\text{Percentage change from baseline} = \frac{(D_i - D_0)}{D_0} \times 100$$

With

D_i the sum of the longest diameters of the target lesions as per RECIST v1.1 at the time point/Visit i .

D_0 the sum of the longest diameters of the target lesions as per RECIST v1.1 at baseline.

- Best percentage change from baseline in sum of target lesions longest diameters, calculated as:

$$\text{Best percentage change from baseline} = \frac{(D_{min} - D_0)}{D_0} \times 100$$

With:

D_{min} the minimum sum of the longest diameters as per RECIST v1.1 on all measurement time points.

D_0 the sum of the longest diameters of the target lesions as per RECIST v1.1 at baseline.

Correlations will be computed between dosimetry parameters (cumulative absorbed dose) and volume and diameter changes in lesions at the last visit of the core trial (EOCT or EACT or EW as applicable).

(b) Progression Free Survival (PFS)

PFS will be evaluated up to two years after the EOCT/EOAC Visit and will be based on RECIST v1.1 status assessed by investigator assessment. PFS will be assessed by independent central review up to EOCT/EOAC/EW Visit (during the core study part).

PFS is defined as the time from start of study treatment until occurrence of tumour progression or death.

(c) Quality of life using EORTC QLQ C30 v3.0 and QLQ GLNET21 (2006) questionnaires.

- EORTC QLQ C30 v3.0

The European Organisation for Research and Treatment of Cancer (EORTC) score questionnaire (QLQ-C30) will be used for quality of life (QoL) evaluation.

Following the EORTC recommendations, fifteen scales can be derived from the initial 30 questions:

- A global health status/QoL scale,
- Five functional scales (physical, role, cognitive, emotional and social),
- Nine “symptoms” scales /items (nausea and vomiting, pain, fatigue, dyspnoea, insomnia, appetite loss, constipation, diarrhoea and financial difficulties).

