For investigator data, the DCR rate at selected timepoints (Month 12, 18, 24) will also be generated. For DCR at month 12 (resp. 18 and 24 month), the analysis will include all patients who are on study at month 12 (resp. 18 and 24 month) defined as 365 days – 28 days (resp. 545 - 28 and 730- 28) relative to the first dose or patients who had early PD or death prior to that time. The best overall response category of CR, PR or SD in patients who have not had an early PD or death up to the timepoint will represent the subjects with disease control

c) Sum of Diameters

Descriptive statistics and 95% CIs of the mean for percentage change from baseline will be calculated by study part, cohort (part B only) and overall at Follow-up Visit 2, EOCT, EOAC (if any) and Long-Term Follow-up visits on the ITT and PP sets. The length of the longest diameter will also be presented.

Percent change and best percent change in sum of diameters will be listed.

Percent change of sum of diameters according to RECIST ^{CCI} will also be plotted by study part and cohort (part B only) at Visit 2, EOCT Visit, EOAC Visit (if any) and Long-Term follow up visits 1 and 2 on the ITT set.

Waterfall plots presenting best overall response (RECIST ^{CCI}) versus best percent change from baseline of sum of target lesion diameters over the whole study will be performed on the ITT set.

d) Progression Free Survival (PFS) from independent central review and from investigator assessment

PFS, defined as the time from first study drug administration to progression or death which ever occur first, will be analysed.

Disease progression will be assessed by tumour response evaluation according to RECIST v1.1/ ^{CCI}, measured using the same imaging technique (ceCT scan or MRI) for each subject throughout the study.

Event dates are assigned to:

- The first time when progressive disease was noted, or
- Date of death.

In case of progressive disease followed by death, the first event will be considered in the analysis. The date of progression will be recorded as the date of the last radiographic evaluation included in the series for that assessment.

Censoring dates are defined in subjects with no progressive disease or death before end of study or withdrawal. In these subjects, the censoring date is defined as the last date on which overall

RECIST status was evaluable. This is taken to be the date of the last radiological assessment at which the target lesions were evaluated (see Table 7).

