Table 7 Censoring Rules for PFS

Reason for censoring	Rule
No screening evaluable[a] assessment	Date of first treatment administration
Two or more not evaluable (NE) consecutive assessments before progressive disease or death	Date of last evaluable disease assessment before the second NE assessment
No progressive disease	Date of last evaluable disease assessment
Treatment discontinuation for undocumented progression	Date of last evaluable disease assessment
Treatment discontinuation for toxicity or other reason	Date of last evaluable disease assessment
Initiation of medications or therapy not permitted during the study	Date of initiation of non-permitted medication or therapy

a An assessment is considered NE when no imaging/measurement is done at all at a particular time point, or only a subset of lesion measurements are made at the time point. The subject is considered NE at that time point.

For central reading assessments, patients will be censored at the timepoint of the last central assessment at or before EOCT/EOAC.

The PFS time will be calculated as the time from first administration of the study drug to either progressive disease or death as follows.

$$\text{PFS time (in months)} = [(\text{Date of event} - \text{date of first administration of study drug} + 1) / 30.4375]$$

Data will be analysed by study part, cohort (part B only) and overall part B on the ITT and PP sets. The distribution of PFS times will be estimated using the Kaplan Meier method for each study part, cohort (part B only) and overall Part B. The median PFS time will be presented with its associated 95% CI, together with the number and percentage of events, by study part, cohort (part B only) and overall. The results will also be presented graphically in Kaplan Meier plots.

Completely missing tumour data: when tumour assessment visits are completely missing, FDA Guidance “Clinical Trial Endpoints for the Approval of Cancer Drugs and Biologics” [4] states that "events occurring after two or more missed radiological assessments will be censored in the analysis at the last adequate assessment”.

This will be implemented as follows:

[figure not shown]

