DoR refers to the time when complete response (CR) or partial response (PR) is first observed until the time of progressed disease (PD) or death for the subjects whose best overall response is complete response (CR) or partial response (PR). If the subject did not have an event of PD or death, then DoR will be the time of last tumor assessment.

DoR will be listed.

Summaries of DoR will include summary statistics of duration, the number and the associated percentage of patients whose DOR is >3, >6, >9 and >12 months for Part A and Part B and overall (Part A and B). In case of sufficient responders, the median of DOR (calculated based on Kaplan-Meier) and 95% confidence interval of median time will also be summarized.

h) Tumour Volume (mL)

Tumour Volume (mL) is measured for each lesion at each scheduled visit by independent central review using RECIST (v1.1) and CCI. The sum of the tumour volume (mL) per visit will be computed and descriptive statistics of tumour volume, change in tumour volume and percentage change in tumour volume will be generated at each scheduled visit on the ITT and PP sets.

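### As written, the best percentage change formula lets baseline into the minimum, so a subject whose target lesions only grew is shown as 0%

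*SAP*

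**What the plan says.** SAP 3.1.6, under the sum of diameters, gives two derivations. The change at visit i is (D_i − D_0)/D_0 × 100. The best change is (D_min − D_0)/D_0 × 100. D_0 is "the sum of the longest diameters of the target lesions as per RECIST v1.1 at baseline", and D_min is "the minimum sum of the longest diameters as per RECIST v1.1 on all measurement time points". No words limit D_min to visits after treatment starts or to scans with all target lesions measured.

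SAP 1.3.2.2 says that target lesions "should be identified as target lesions and recorded and measured at baseline". It also fixes what enters the sum: "A sum of the diameters (longest for non-nodal lesions, short axis for nodal lesions) for all target lesions will be calculated", and again, "If lymph nodes are included in the sum, then only the short axis will be added into the sum". Protocol 11.4.8 has the same nodal rule.

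Footnote a to Table 7 (SAP 3.2.3) treats a time point as not evaluable when there is no imaging "or only a subset of lesion measurements are made at the time point". That table governs PFS censoring. Table 4 (SAP 3.1.6) makes the time point response NE when the target lesions are NE, the non-target lesions have not progressed and there is no new lesion.

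Best percent change is listed. It also goes into waterfall plots of best overall response "versus best percent change from baseline of sum of target lesion diameters over the whole study will be performed on the ITT set" (SAP 3.2.3 c).

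**The concern.** Baseline is a measurement time point. If it is eligible for the minimum, D_min can never exceed D_0 and the best change can never be positive. A subject whose lesions grew at every scan gets a bar at zero, the same as a subject with no change. The waterfall plot would then have no upward bars, and the display would look better than the data. Most Part B cohorts have three to five subjects (SAP 1.2.1.2), so one such bar is between 1/5 = 20% and 1/3 = 33% of a cohort's picture.

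Elsewhere the SAP writes the limit in when it wants one. BOR runs from the start of treatment (3.1.6), and laboratory shift tables use the worst value after baseline (3.2.1.3). It also sets completeness rules for other derived values: cumulative dose is missing if any one administered dose is missing (3.2.1.7), and a quality-of-life scale needs at least half of its items (3.1.6). D_min has neither kind of rule.

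**Working it through.** The documents state no figure for this endpoint, so there is none to reproduce. All lesion sizes, growth rates and SDs below are assumptions; the formula is the SAP's.

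**1. Baseline in the minimum.** Sums of 100 (baseline), 110 and 125 mm.
- Baseline included: D_min = 100, so (100 − 100)/100 = 0%.
- Post-baseline only: D_min = 110, so (110 − 100)/100 = +10%.
- A subject who shrinks is unaffected. Sums of 100, 85 and 90 mm give −15% either way.

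**2. How many subjects this could touch.** A subject is affected when every post-baseline sum exceeds baseline. I assumed log-normal measurement error on every scan including baseline, with SD 10%/√2 ≈ 7.1% per scan so that the change has SD 10%. I assumed three post-baseline scans, as in the Part B core period (Visits 2 and 3 and EOCT).

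| Assumed trend per interval | Subjects with only positive changes |
|---|---|
| +5% | 61% |
| 0% | 25% |
| −2% | 12% |
| −5% | 2% |

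The zero-growth figure can be checked by hand: the four scans are then exchangeable, and baseline is the smallest with probability 1/4. At +5% growth the mean best change is −2.4% with baseline included and +2.9% without. If all the error is placed on the follow-up scans, the 61% becomes about 53%.

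**3. Nodal wording.** A single nodal target lesion goes from 24 × 16 mm to 20 × 11 mm.
- Longest diameter: (20 − 24)/24 = −17%.
- Short axis: (11 − 16)/16 = −31%.

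With non-nodal disease alongside, the gap narrows. Take non-nodal lesions from 70 to 60 mm, with a node whose long axis goes from 28 to 22 mm and short axis from 18 to 9 mm. The long axis gives (82 − 98)/98 = −16.3% and the short axis (69 − 88)/88 = −21.6%.

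**4. Partly measured scan, if its sum were used.** One of k equal, unchanged lesions is not measured. The apparent change is −1/k: −50% for k = 2, −33.3% for 3, −25% for 4 and −20% for 5. If only fully measured scans count, the change is 0%.

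**5. Where D_min goes.** It goes to the best-change listing and the waterfall plots. The mean change with its 95% CI is computed visit by visit (SAP 3.2.3 c), and the correlations with absorbed dose use changes at the last core-trial visit (SAP 3.1.6). Neither uses D_min.

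**The case against.** The best case for the plan is that no sentence puts baseline into the minimum. SAP 3.1.6 defines the baseline sum separately from the sum at visit i, so D_min can be read as the lowest D_i, and a change from baseline is not naturally a comparison of baseline with itself. That reading is reasonable, but the text does not state it. A programmer working from the derivation must choose, and the literal choice caps the result at zero.

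Three stronger readings are tempting, and the documents do not support them.

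- *The plan adds up long axes of nodes.* Each definition says it follows RECIST v1.1, and SAP 1.3.2.2 and protocol 11.4.8 require the short axis explicitly. This is conflicting wording, not a different rule.
- *The plan counts unmeasured lesions as shrinkage.* No sentence says a partial sum is used. The sums are defined over the target lesions, and a subset scan is classed NE for PFS. The gap is that this rule is not carried over to the sums. Nor can the point be extended to tumour volume. The SAP says that "The sum of the tumour volume (mL) per visit will be computed", but from volumes measured for each lesion at each scheduled visit by central review.
- *The baseline problem distorts the mean changes, the dose correlations or the response rates.* It does not, because none of them uses D_min.

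Two more points stand. The waterfall plot also presents best overall response, so a subject with progression as best response is still identified as such. And growth in every subject is an unfavourable base case: in the earlier investigator study in protocol 1.4, 3 of 19 subjects (16%) progressed.

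**Conclusion.** The defect is real but minor. As written, D_min admits baseline, and a subject with growth only is then shown at 0% in the best-change listing and waterfall plots. The reference to longest diameters conflicts with the nodal rule stated elsewhere in both documents. Because that phrase also appears in D_i and D_0, it needs correcting there too. A partial sum is not excluded from the minimum, although nothing says it is included.

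The cap at zero follows from the literal wording and needs no assumption about tumours. The share of subjects affected does need one: it runs from about 2% to 61% across the assumed trends, and the documents give no growth rate or SD to narrow it. BOR, ORR, DCR and PFS are untouched, and the study is descriptive with no formal testing.

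**What to change.** In SAP 3.1.6, define D_i, D_0 and D_min as the RECIST v1.1 sum of diameters: longest diameter for non-nodal target lesions and short axis for nodal ones, matching SAP 1.3.2.2. Define D_min as the minimum over post-baseline time points at which all baseline target lesions were assessed. It would help to add that a lesion that was looked for and has disappeared counts as assessed, and to footnote the number of subjects with no qualifying scan.

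The cost is a wording change and a small amount of programming, with no new data. The downside is that a few time points with unmeasured lesions leave the plot.

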Cohorts 3 and 6 will require 8 subjects to ensure there is sufficient power to demonstrate any tumour sstr2 saturation. Therefore 10 subjects will be enrolled to obtain a minimum of 8 completed subjects. All remaining cohorts (1, 2, 4, 5, 7 and 8) will enrol three to five subjects to obtain a minimum of three completed subjects per cohort.

Hence, it is anticipated that 10 subjects will be enrolled in Cohorts 3 and 6, and five subjects will be enrolled in Cohort 1, so the end-point can be achieved in these initial three cohorts rapidly (total of 25). To maintain the subject numbers to a maximum of 40 in Part B, if all remaining cohorts are utilised (total of five), each will have three subjects enrolled (total of 15).

Change in eligibility criteria for Part B

To ensure sufficient precision for the imaging dosimetry (specifically in Cohorts 3 and 6, but also for the whole study), eligibility will require a minimum of two lesions ≥ 20 mm in diameter. Tumour dosimetry should be performed on tumour lesions identified by the imaging core laboratory and on no more than five lesions (maximum two per organ, size ≥ 20 mm diameter, accessible for dosimetry). Furthermore, this ensures the modelling is based on a minimal total receptor burden.

Infusion rate

The i.v. infusion of ^{177}Lu -OPS201, should be at a rate of 10 mL/h over 120 minutes (see Section 6.2.1).

Investigators are advised that prophylaxis may be considered if the patient is thought to be at increased risk of infusion-related reactions as per the site's standard of care (see also 6.3.3 and Section 6.3.4). Appropriate treatment should be administered should an infusion-related reaction occur including somatostatin analogues. The administered radioactivity and mass dose follows the escalation scheme (see Section 6.2).

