3.1.5 Additional Optional Cycles, Part B

If a subject tolerates the treatment well and shows clinical benefit (e.g. CR, PR, or SD) up to two additional cycles at a radioactivity dose adjusted based on dosimetry results can be administered to this subject provided limiting organ absorbed dose levels have not been exceeded. Two cycles would consist of ^{177}Lu -OPS201 administration every 8 weeks ($+2$ weeks, or plus up to 4 weeks in case of AEs which are not adequately recovered) with administration of the same peptide mass dose as Cycle 1. In this case, subjects will have the same assessments as during the core treatment cycles and up to EOAC or EW except for exploratory biomarkers **CCI**. Dosimetry will thus be performed after each additional cycle to prevent exceeding limiting organ absorbed doses. For these subjects, an EOAC visit will be done 8 weeks (± 5 days) after the last ^{177}Lu -OPS201 dose administration. In this case, the 2-year long-term follow-up will start at the EOAC (instead of EOCT).

The decision to administer additional cycles or any other antitumoural treatment is at the investigator's and subject's discretions and must be discussed with and confirmed by the sponsor. However, the investigator should follow the following rules before proceeding to any additional administration:

- subjects with DLTs after first, second or third administration will be discontinued from ^{177}Lu -OPS201.
- subject will be eligible for an additional administration of ^{177}Lu -OPS201 only if:
 - renal function and blood cell counts are in the range defined in the study inclusion criteria (#12 and #13), within the treatment cycle.
 - organ absorbed doses did not exceed 1.5 Gy in bone marrow (BM) and 23 Gy in kidneys.
 - subject is likely to benefit from additional cycles of ^{177}Lu -OPS201 therapy.

The planned maintenance dose for any cycle may be adjusted such that the limiting organ absorbed doses are not exceeded.

Subjects who are to receive additional cycles of therapy will undergo the EOCT assessment

after Cycle 3. Where possible, the EOCT visit and Visit 4, Day 1 of the first additional cycle can be combined. An additional EOAC assessment will be done 8 weeks after the last dose of therapy.

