3.1.3 Radiation dosimetry endpoint(s)

Radiation dosimetry endpoints are the following (calculations methods are described in the Dosimetry Calculation Procedure Manual):

- (a) Absorbed dose in organs/ lesion (unit: Gy).

- (b) Specific absorbed dose to the lesions (unit: Gy/GBq)

The specific absorbed dose to the lesions is the absorbed dose by the lesion (unit: Gy) divided by the injected radioactivity (unit: GBq) for each lesion selected for dosimetry evaluation.

Specific absorbed dose to the lesions (unit: Gy/GBq) will be computed for each administration of ^{177}Lu -OPS201 (visits 1, 2 and 3) on part A, and on Part B (Cohort 1, 3 and 6), for each lesion lesion evaluable in dosimetry (all lesion and by lesion location) when at least 3 patients in the same cohort is having a lesion in the same organ, by visit and overall.

- (c) Specific absorbed dose per organ (unit: Gy/GBq).

The specific absorbed dose for a given organ is the absorbed dose by this organ (unit: Gy) divided by the injected radioactivity (unit: GBq).

Specific absorbed dose per organ (unit: Gy/GBq) will be computed for each administration of ^{177}Lu -OPS201 (visits 1, 2 and 3) and any additional cycle.

- (d) Cumulative absorbed doses in organs and lesions selected for dosimetry evaluation (unit: Gy).

The cumulative absorbed organ dose is calculated as the sum of the absorbed dose over all the ^{177}Lu -OPS201 administration cycles. In case absorbed dose is missing for at least one of the ^{177}Lu -OPS201 administration cycles, cumulative absorbed dose is extrapolated from available data at the other cycles by dosimetry expert.

Cumulative absorbed doses will be provided per organ and for lesions selected for dosimetry evaluation.

CCI

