Progressive Diseases (PDs) occurring after two or more missed radiological assessments will be censored in the analysis at the last adequate* assessment before the missing assessments: If a subject has one missed radiological assessment before a PD, the PD will be analysed as an event (i.e. a PD is analysed as an event if the previous radiological assessment was performed within approximately the last 6 months).

Table 8 Event status for various scenarios with missing data

Scan Time	FU Visit 2	EOCT/EOAC / EW Visit	Long-term Follow-up Visits n	Long-term Follow-up Visits n +1	Event status
Scenario 1	missing	PD			Event at EOCT/EOAC/EW visit
Scenario 2	missing	missing	PD		Censored at Baseline
Scenario 3	missing	SD	PD		Event at Long-term Follow-up Visit n
Scenario 4	missing	missing	SD	PD	Event at Long-term Follow-up Visit n+1
Scenario 5	SD	SD	missing	PD	Event at Long-term Follow-up Visit n+1
Scenario 6	SD	missing	missing	PD	Censored at FU Visit 2

e) Dosing and dosimetry in conjunction with tumour burden

A figure depicting the following relationship displaying the Pearson’s correlation coefficient (and the associated 95% confidence interval):

- CCI
 -
- 

f) Quality of life

- EORTC QLQ C30 v3.0

For QLQ C30 global health status score, functional scales scores and symptom scales scores, descriptive statistics and 95% CIs of the mean will be presented for the raw data and for the changes from baseline during treatment, by study part, cohort (part B only) and overall at each visit (Visit 1, 2, 3, optional visits (if any) and EOCT/EOAC Visits) on the ITT and PP sets.

For the evaluation of the QLQ C30 scores values at baseline the EORTC QLQ C30 Reference Values manual (Ref. 12) or a more up to date reference will be used.

- EORTC QLQ – GI.NET21 (2006)

For GI.NET21 endocrine symptoms scale score, G.I. symptoms scale score, treatment related symptom scale score, social function scale score, disease related worries scale score, muscle /bone pain symptom item, sexual function item, information/communication function item and body Image item, descriptive statistics and 95% CIs of the mean will be presented for the raw data and for the changes from baseline during treatment, by study part, cohort (part B only) and overall at each visit (Visit 1, 2, 3 and EOCT Visit) on the ITT and PP sets.

g) Duration of Response (DoR)

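### The planned correlation of cumulative lesion dose with tumour change at the last visit lets response influence dose, so it leans towards more dose, more shrinkage even when dose has no effect

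*SAP*

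**What the plan says.** - **The analysis.** SAP 3.1.6, under the sum of diameters: "Correlations will be computed between dosimetry parameters (cumulative absorbed dose) and volume and diameter changes in lesions at the last visit". The sentence goes on to limit this to the core trial and names the visit as "EOCT or EACT or EW as applicable". The abbreviation EACT is defined nowhere in the visible text.
- **The exposure.** SAP 3.1.3(d) has cumulative dose "calculated as the sum of the absorbed dose over all the" administration cycles, and adds: "Cumulative absorbed doses will be provided per organ and for lesions selected for dosimetry evaluation".
- **The interval.** SAP 3.2.3(e) plans a figure with Pearson's "correlation coefficient (and the associated 95% confidence interval"). The relationships listed beneath it are redacted.
- **The number of lesions.** Part B subjects need at least two qualifying lesions (Protocol 4.1, criterion 11). Lesion dosimetry is done "on no more than five lesions (maximum two per organ"; Protocol 3.1.3).
- **Who gets more cycles.** Protocol 3.1.5 opens the optional Part B cycles to a subject who tolerates treatment and "shows clinical benefit (e.g. CR, PR, or SD) up to two additional cycles". For core cycles, Protocol 4.6.1 lets the investigator withdraw a progressing subject who is not expected to benefit. Protocol 3.1.2 counts a subject who stops early for progression as completed, and 4.6.1 does not replace that subject.
- **Adjustment and status.** SAP 3.2.20 plans no covariate adjustment. SAP 3.1.9 plans no formal testing and treats any p-value as exploratory.

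**The concern.** A dose-response correlation can be read as such only if the response does not determine the dose. Here it partly does. A subject whose lesions grow may stop after one or two cycles, and so combines a low cumulative dose with growth. A subject with disease control completes three cycles, or up to five in Part B, and so combines a high cumulative dose with stability or shrinkage. That pattern arises even if dose does nothing. Time from baseline to the last scan varies with the number of cycles as well.

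A second problem applies only if each lesion is one data point. Lesions in one subject share that subject's biology and administered radioactivity, and a standard Pearson interval treats them as independent.

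Evaluating the optimal radioactivity for future studies is a secondary objective (Protocol 2.2), and Protocol 2.1 wants a recommended cumulative radioactivity. A figure tilted towards higher cumulative dose could mislead a reader with that question in mind.

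**Working it through.** The documents give no expected correlation, power or error rate for this analysis, so there is no figure to reproduce. I checked it by simulation under a true dose effect of zero.

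**Inputs from the documents:** three core cycles and up to two more in Part B; 2 to 5 lesions per Part B subject; up to 40 subjects in Part B and 55 in all; cumulative dose summed over cycles given.

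**Inputs assumed:** 3 lesions per subject; dose per cycle log-normal around 30 Gy, log-SD 0.6, within-subject correlation 0.5; log-diameter change per cycle with mean −0.08, −0.05 or 0, between-subject SD 0.10 and within-subject SD 0.07; measurement SD 0.05; 10% stopping per cycle for other reasons; progression taken as a sum of diameters at least 20% above baseline.

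**Model.** With c cycles received, per-cycle dose d and per-cycle change g, where d is independent of g:

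- X = c × d
- Y = 100 × [exp(c × g + error) − 1]

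X and Y are linked only through c, which depends on g when progression stops treatment or when extra cycles need disease control.

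**Illustration, ignoring error.** Take two lesions with the same d = 30 Gy.

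- g = +0.10 (1.5 between-subject SDs above a mean of −0.05): exp(0.10) = 1.11 after one cycle and exp(0.20) = 1.22 after two. If the subject stops there, X = 60 Gy and Y = +22%.
- g = −0.05: three cycles, X = 90 Gy, Y = 100 × [exp(−0.15) − 1] = −14%.

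The dose per cycle is identical, yet the pair shows a dose effect.

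**Simulation.** There were 4,000 trials per setting, N = 40, with a Fisher-z 95% interval. Ranges are over the three mean growth rates. Negative r means more dose, more shrinkage.

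| Setting | Mean r, lesion level | Interval excludes 0, lesion level | Interval excludes 0, subject level |
|---|---|---|---|
| All stop at progression, no extra cycles | −0.090 to −0.115 | 22.5–28.4% | 10.5–18.0% |
| All stop, half of eligible subjects take extra cycles | −0.168 to −0.183 | 46.8–52.5% | 31.2–39.7% |
| Half stop at progression, no extra cycles | −0.046 to −0.063 | 14.6–18.3% | 6.8–8.1% |
| None stop for progression, no extra cycles | −0.032 to +0.014 | 12.3–13.8% | 4.8–5.1% |

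Monte Carlo standard error is about √(0.25 × 0.75 / 4000) = 0.7 percentage points near 25%. The last row is almost entirely clustering. The subject-level column isolates the dependence of dose on response.

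**More subjects do not help.** With mean change −0.05, lesion level and all stopping, the rate without and with extra cycles is 17% / 28% at N = 15, 20% / 37% at 25, 25% / 49% at 40 and 28% / 59% at 55.

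**Clustering cross-check.** The design effect is 1 + (m − 1) × ICC(dose) × ICC(change). With m = 3 and both ICCs 0.5 it is 1 + 2 × 0.25 = 1.5. The two-sided error is 2 × [1 − Φ(1.96 / √1.5)] = 11.0%, against 11.6% simulated with Cycle 1 dose and the first scan.

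**Effect of the repair.** Cycle 1 dose against change at the first scan, one value per subject, gave mean r of about 0 and 4.5–5.4%. Half a repair is not enough:

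- Fixing the time point but keeping lesions as independent units leaves 7–11% with 2 lesions, 8–15% with 3 and 12–22% with 5.
- Fixing the unit but keeping cumulative dose at the last visit leaves 13% without extra cycles and 32% with them (N = 40, mean change −0.05, all stopping).

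**The case against.** Several stronger readings are tempting, and the documents do not support them.

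- **That progression ends treatment.** It is not in the mandatory stop lists of Protocol 6.4.1 and 6.4.2; core-cycle withdrawal for progression is discretionary. In Part A no CT/MRI is scheduled between screening and Follow-up Visit 2, so scheduled imaging cannot stop a subject after Cycle 1. The dependence is explicit only for the optional Part B cycles.
- **That five-cycle doses certainly enter.** SAP 3.1.6 speaks of the core trial, and EACT is undefined. This does not clear the plan, however: if change is read at EOCT while dose is summed over all cycles, part of the dose was given after the response and because of it.
- **That a Pearson interval is applied to lesion pairs.** SAP 3.1.6 names no coefficient, interval or unit. The variables in SAP 3.2.3(e) are redacted, the diameters in SAP 3.1.6 are sums per subject, and SAP 3.2.3(h) also sums volumes per visit. The SAP contents list a modelling section whose text is not visible, and clustering may be handled there. The reference to changes in lesions makes the lesion-level reading reasonable, not established.
- **That it drives the dose decision.** Protocol 3.8 bases escalation primarily on clinical and safety data, with rules on dose-limiting toxicity and organ dose. The correlation is exploratory.

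It is also fair that the EOCT, EOAC and EW scans all fall 8 weeks after the last dose. Time from last dose is therefore aligned, and only time from baseline differs.

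What stands is that the exposure depends partly on the outcome, no common time point is set, the unit is unstated in the visible text, and no adjustment is planned.

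**Conclusion.** The concern holds in a limited form. The bias towards more dose, more shrinkage follows from the visible text, and confidence in its direction is high. The narrow interval is conditional on a lesion-level analysis, and confidence there is moderate.

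The size is a range, not one figure. For a nominal 5% at N = 40, it is about 7–18% at subject level and 15–28% at lesion level without extra cycles, with half to all subjects stopping at progression. It is about 47–53% at lesion level if extra cycles enter and all stop at progression. A reader might take the top of that range as the plan's error rate. That would need extra-cycle doses to count, every progressing subject to stop, and lesions to be analysed as independent, and the documents establish none of the three.

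All rates rest on the stated assumptions. With no stopping for progression and no extra cycles, the subject-level analysis keeps its nominal rate. The harm is a misleading exploratory estimate and interval, not a false result in a formal test. It should be corrected because the data for a sounder analysis are already collected.

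**What to change.** 1. **Fix the exposure before the response is read, by study part.** For the correlation that carries an interval:
   - Part B: Cycle 1 lesion dose against change at the Visit 2 scan, which precedes the second administration.
   - Part A: lesion dose from Cycles 1 and 2, or mean dose per cycle, against change at the Follow-up Visit 2 scan. Cycle 1 dose alone would not match, because that scan follows two administrations.
2. **State the unit of analysis.** Use one value per subject (mean over lesions), a lesion-level mixed model with a subject random effect, or an interval from a bootstrap that resamples subjects.
3. **Keep the cumulative-dose, last-visit plot as a display only.** Label points by number of cycles and give no interval. Define EACT, and say whether doses from additional cycles count.

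The cost is SAP wording and minor programming, with no new data. The simulated repair used the Part B arrangement; the Part A version rests on the same reasoning but was not simulated. The downside is real: change is read early in tumours that the protocol describes as mostly slow-growing, so the correlation will probably be weaker and the interval wider.
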